6.2.4. Duration

Duration of double-blind treatment will be determined as Double-Blind Duration = Double-Blind Last Dose Date minus Double-Blind First Dose Date plus 1. Duration of Run-In period will be determined as Duration = Last Dose Date in the run-in period minus First Dose Date in the run-in period plus 1.

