6.2.7. Intensification of Hypoglycemic Agent Use

Intensification of hypoglycemic therapies should be considered if one or more of the following:

1. A new oral hypoglycemic therapy is added to the prior medication.
2. An increase of dose in any of the prior oral therapies.
3. A new injectable non-insulin hypoglycemic therapy is added to the prior medication.
4. An insulin therapy is initiated in addition or in place of oral hypoglycemic therapy (ies).
5. An increase of ≥ 5 units total daily dose of insulin any time during the treatment period

The following scenarios are NOT considered intensification:

1. A replacement of a sulfonylurea or insulin with an injectable GLP-1 agonist;

2. An increase of < 5 unit of insulin total daily dose;
3. Any increase of the therapy use after the last day of investigational product administration;
4. Insulin dose usage as needed or pro re nata (PRN) will be considered the same dose;
5. A short course treatment of insulin or other therapies to manage an acute illness.
6. An intensification after relaxation will not be considered as intensification.

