6.2.8. Relaxation of Hypoglycemic Agent Use

Relaxation of hypoglycemic therapies should be considered if one or more of the following:

1. Stop or decrease dose of one or more oral hypoglycemic therapies occur during the double-blind treatment period;
2. A decrease of ≥ 5 unit total daily dose of insulin any time during the treatment period.

The following scenarios are NOT considered relaxation:

1. A decrease of hypoglycemic therapies after an intensification of hypoglycemic therapy use.
2. Stopping of a short course of hypoglycemic therapy use.

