8.1.1. Primary Efficacy Analysis

Let $\mu_{\text{Bexagliflozin}}$ and μ_{PBO} represent the mean changes from baseline in HbA_{1c} at Week 24 for bexagliflozin and placebo arms, respectively. The following hypotheses will be tested:

$$H_0: \mu_{\text{bexagliflozin}} - \mu_{\text{placebo}} \geq 0$$

$$H_a: \mu_{\text{bexagliflozin}} - \mu_{\text{placebo}} < 0$$

Missing data will be imputed via multiple imputations, following which the MMRM will be repeated on the complete datasets with results combined across complete datasets using standard multiple imputations techniques; HbA_{1c} values collected after the start of intensification of hypoglycemic agent will not be excluded. A pattern-mixture model will be used to explore the impact of the missing data. Imputation will be conducted within each treatment arm and subgroup (treatment completer vs. treatment terminated early) under the assumption that non-adherent subjects with missing data will follow the same trajectory of non-adherent subjects with values observed. All efforts will be made to retain subjects in the study. If treatment is discontinued, subjects are encouraged to remain in the study and complete all scheduled visits, including final follow-up visit. However, with all efforts, insufficient values may be available for reliable imputation. This analysis will be performed only if at least 5 subjects in each treatment arm completed scheduled week 24 visit after treatment is stopped. This number is chosen to allow sufficient data to establish a regression model for imputation. For this analysis, the following three-step approach outlined below will be used:

- a. Non-monotone (intermediate visits) missing data will be imputed first using the Monte Carlo Markov Chain (MCMC) method under the MAR assumption in all treatment arms (using the MCMC statement in PROC MI). Multiple chains option

(CHAIN=MULTIPLE option in the MCMC statement of PROC MI) will be used. For the non-monotone imputation of the HbA_{1c} missing data, a multivariate normal model will be used including variables for the HbA_{1c} at baseline and all post-baseline visits within each treatment group. Five hundred imputed datasets will be generated.

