8.2.2.6. Time to first use of intensification or relaxation of hypoglycemic agent

Kaplan-Meier plots will be prepared for these endpoints by treatment. These endpoints will be analyzed using Cox proportional hazards models with treatment, region, baseline eGFR categories (<60 or ≥60 mL min⁻¹ per 1.73 m²), baseline BMI (< or ≥25 kg m⁻²), history of heart failure (yes or no), insulin use or not, and baseline HbA_{1c} as the covariates. Maximum likelihood with ties method of Breslow will be used. The hazard ratio of the endpoint, p-value with its two-sided 95% CIs presented. Subjects who withdraw from the trial and have post-baseline assessments will be censored at the last contact date. Subjects who have no follow-up event data will be censored at the date of randomization + 1 day. Analysis will also be conducted for subjects who have been prescribed insulin or sulfonylurea to control their diabetes. Time to first intensification of hypoglycemic agent will also be conducted for subjects who have been prescribed insulin or sulfonylurea to control their diabetes.

8.2.2.7. Time to hospitalization for heart failure and time to cardiovascular death or hospitalization for a heart failure event in all subjects and in subjects with a history of heart failure

Same analyses in Section 8.2.2.6 will be conducted. History of heart failure will not be used in the analysis model in subjects with a history of heart failure.

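### The Cox analysis of time to intensification or relaxation keeps subjects at risk after the event can no longer be counted, and the SAP does not say which hazard ratio is meant

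*Combined protocol and SAP*

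**What the plan says.** **Event definitions.** SAP 6.2.7 has two numbered lists; the second gives scenarios that are not intensification. Its item 3 is "Any increase of the therapy use after the last day of investigational product administration" and its item 6 is "An intensification after relaxation will not be considered as intensification". The second list in SAP 6.2.8 (what is not relaxation) opens with "A decrease of hypoglycemic therapies after an intensification of hypoglycemic therapy use". The first list in 6.2.8 also limits relaxation in time. Oral changes count under "Stop or decrease dose of one or more oral hypoglycemic therapies occur during the double-blind treatment period", and insulin decreases of 5 units or more count if they fall within the treatment period. SAP 6.2.4 says: "Duration of double-blind treatment will be determined as Double-Blind Duration = Double-Blind Last Dose Date minus Double-Blind First Dose Date plus 1".

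**Analysis.** SAP 8.2.2.6 fits Cox models to both endpoints with two censoring rules: "Subjects who withdraw from the trial and have post-baseline assessments will be censored at the last contact date" and "Subjects who have no follow-up event data will be censored at the date of randomization + 1 day". It calls the result only the hazard ratio of the endpoint. Protocol 9.6.2 adds that subjects lost to follow-up are censored at last known follow-up.

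**Follow-up after stopping study drug.** SAP 8.1.1 states: "If treatment is discontinued, subjects are encouraged to remain in the study and complete all scheduled visits". SAP 6.2.5 defines end of study as the date of final contact, not the last dose.

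**The concern.** A Cox model compares events per unit of time at risk, so a subject should normally be in the risk set only while an event could be recorded. Here the definitions close the window for intensification at the last dose or at a first relaxation, and for relaxation at a first intensification. The censoring rules let the clock run to last contact. A subject who stops study drug but stays in the study, or whose first change is in the other direction, adds time at risk and can add no event.

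Keeping subjects in this way dilutes the rate in each arm according to how often the window closes early. If that frequency differs between arms, the hazard ratio mixes the effect on intensification with the effect on relaxation or on stopping. Two programmers could follow 8.2.2.6 faithfully and report different numbers, and a reader could not tell which quantity was estimated.

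**Working it through.** The plan gives no event rate, power or expected hazard ratio for these endpoints, so there is no figure to reproduce. The check asks how far apart two readings of 8.2.2.6 can lie.

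**Inputs from the documents:** 1100 versus 550 subjects and 6.5% annual withdrawal (SAP 3.7); follow-up of 1 to 3 years (SAP 3.7) or an anticipated 2 to 3 years of treatment (Protocol 3.2.2).

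**Assumptions:** constant, independent hazards. Intensification is a = 0.25 per year in both arms, so the true cause-specific hazard ratio is 1.00. The window closes at rate k per year, through relaxation or through stopping study drug, taken one at a time. Follow-up is uniform over the stated range, withdrawal is a hazard of 0.065, and the model has treatment only.

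**Formulas.** Without withdrawal, at time t:
- share still able to have a countable event: E = exp(−(a+k)t)
- share already counted: F = a/(a+k) × (1 − E)
- share in the risk set under last-contact censoring: 1 − F
- apparent hazard: a × E/(1 − F)

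**Worked example at 2 years, relaxation 0.05 (placebo) versus 0.10 (active):**
- Placebo: E = exp(−0.60) = 0.549; F = (0.25/0.30) × 0.451 = 0.376; 1 − F = 0.624; apparent hazard 0.25 × 0.549/0.624 = 0.220.
- Active: E = exp(−0.70) = 0.497; F = (0.25/0.35) × 0.503 = 0.360; 1 − F = 0.640; apparent hazard 0.25 × 0.497/0.640 = 0.194.
- Ratio at 2 years: 0.194/0.220 = 0.88, although the cause-specific ratio is 1.00. At time zero it is 1.00; the Cox estimate averages over follow-up.

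**Share of person-time in which no event can count**, over 2.5 years: 1 − ∫E dt / ∫(1 − F) dt. For k = 0.05 this is 1 − 1.759/1.882 = 6.6%; for k = 0.10, 12.5%; for k = 0.15, 17.9%; for k = 0.08, 10.2%; for k = 0.12, 14.7%.

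**Limiting Cox hazard ratio** (solution of the partial-likelihood score equation with the inputs above), intensification endpoint:

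| Assumed k per year, placebo vs active | Follow-up 1–3 y | Follow-up 2–3 y | Risk set ended when window closes |
|---|---|---|---|
| Stopping 0.08 vs 0.12 | 0.96 | 0.95 | 1.00 |
| Stopping reversed | 1.04 | 1.05 | 1.00 |
| Relaxation 0.05 vs 0.10 | 0.95 | 0.94 | 1.00 |
| Relaxation reversed (0.10 vs 0.05) | 1.05 | 1.07 | 1.00 |
| Relaxation 0.05 vs 0.15 | 0.90 | 0.88 | 1.00 |
| Relaxation 0.05 vs 0.06 | 0.99 | 0.99 | 1.00 |
| Equal rates | 1.00 | 1.00 | 1.00 |

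For relaxation as the event (0.05 or 0.10 per year in both arms), with intensification as the opposite change at 0.25 on placebo and 0.175 on active, a true 1.00 becomes 1.07 (1–3 years) or 1.09 (2–3 years).

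**The case against.** The strongest reply is that 1.00 is the right answer above only because the cause-specific ratio was taken as the target. Retaining subjects after an opposite change gives something close to a subdistribution hazard ratio, which is a legitimate quantity. Censoring instead is not assumption-free. When intensification and the closing event shared a common glycaemic factor (lognormal SD 0.5 to 1.0), simulated hazard ratios with matched censoring ran from 1.01 to 1.07 for the relaxation differences and 0.97 to 1.03 for the stopping differences, against a true 1.00. This stands: for the opposite change, the request can only be that the SAP declare its choice. It does not remove the mismatch at the last dose, where item 3 ends the window for intensification and the analysis does not.

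The sizes rest wholly on assumed rates, and the larger ones need relaxation two to three times as frequent on active. That also stands; at 0.05 versus 0.06 the shift is about 1%. The missing censoring date for event-free completers is only a wording point, since end of study is the obvious reading.

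Three stronger readings are tempting and not supported:
- A reader might infer that the SAP leaves relaxation after the last dose wholly open. It does not: 6.2.8 ties both oral and insulin relaxation to the treatment period. What is unsettled is whether that means the subject's own dosing, as 6.2.4 suggests, or the trial-level period that ends for everyone together (SAP 3.5, Protocol 6.12).
- A reader might infer that the proportions in 8.2.2.4 are invalid. They are a valid incidence of the first change being in a given direction (for intensification, while on study drug), as 6.2.7 and 6.2.8 define it.
- A reader might infer that the first-direction rules are themselves an error. They are stated openly and avoid counting a return to the previous regimen.

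**Conclusion.** The point holds as a minor one. Following the censoring rules in 8.2.2.6 leaves time in the risk set during which 6.2.7 and 6.2.8 allow no event, and the hazard ratio being estimated is not named. With a true cause-specific ratio of 1.00 and the assumed rates, the intensification hazard ratio would be reported at about 0.95 to 0.96 under the stopping difference, 0.94 to 0.95 under the smaller relaxation difference and 0.88 to 0.90 under the larger. The direction follows the rates, so the two sources can add or partly cancel. There is no shift if the arms have equal rates and the true ratio is 1; with equal rates and a true ratio of 0.70 the shift is trivial (about 0.70 to 0.71).

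SAP 8.2.2 treats these endpoints as exploratory, with nominal p-values and no multiplicity adjustment. The primary and key secondary tests are untouched.

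**What to change.** In SAP 8.2.2.6, for the intensification and relaxation endpoints only:

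1. End intensification follow-up at the earlier of the last study dose and last contact, to match item 3 of the second list in 6.2.7.
2. End relaxation follow-up at the end of the treatment period as used in 6.2.8, and state whether that means the subject's last dose.
3. Declare how the opposite change is handled: censored (cause-specific hazard ratio) or retained (subdistribution-type hazard ratio). Support either with cumulative incidence that treats the opposite change as a competing event.
4. State the assumption that censoring at the last dose, and at the opposite change if used, is non-informative given the covariates.

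Scope the wording explicitly. SAP 8.2.2.7 reuses the 8.2.2.6 analyses for heart-failure hospitalization and cardiovascular death, and last-dose censoring should not carry over to those endpoints.

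The cost is small: a few sentences, an added censoring variable and one cumulative-incidence display. The data exist already, because the last dose date is collected and SAP 8.2.2.2 already classifies time as no change, after relaxation or after intensification. The price is the stated censoring assumption. No event definition or treatment rule changes.

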6.2.8. Relaxation of Hypoglycemic Agent Use

Relaxation of hypoglycemic therapies should be considered if one or more of the following:

1. Stop or decrease dose of one or more oral hypoglycemic therapies occur during the double-blind treatment period;
2. A decrease of ≥ 5 unit total daily dose of insulin any time during the treatment period.

The following scenarios are NOT considered relaxation:

1. A decrease of hypoglycemic therapies after an intensification of hypoglycemic therapy use.
2. Stopping of a short course of hypoglycemic therapy use.

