4.2 Inclusion Criteria

The study population will include:

1. Male or female adult subjects with an age ≥ 40 years
2. Subjects with a diagnosis of T2DM
3. Subjects with HbA1c values of 7.0 – 11%, inclusive
4. Subjects with fasting plasma glucose (FPG) ≤ 300 mg/dL at screening
5. Subjects who have a regimen for treatment of T2DM that has been stable for the past 3 months. A stable regimen is defined as: no changes in dose or frequency of OHAs or GLP-1 agonists, or $< 20\%$ variability in total daily insulin dose.
6. Subjects who present with at least one of the following 3 histories:

Group 1: A history of atherosclerotic vascular disease as defined by one or more of the following: a) myocardial infarction (MI) or ischemic (non-hemorrhagic) stroke > 3 months but ≤ 5 years prior to screening or b) documented history of coronary, carotid, or peripheral arterial revascularization (coronary artery bypass grafting must have occurred ≥ 5 years prior to screening)

Group 2: A history of NYHA class II or class III heart failure ([Appendix 4](#)) at the time of screening. History of heart failure is defined as:

- a documented left ventricular ejection fraction (LVEF) $\leq 40\%$ and no subsequent LVEF $> 40\%$ documented within 6 months of screening, or
- (i) an NT-proBNP > 300 pg/mL and no evidence of atrial fibrillation/flutter (AF) at the time of the screening ECG or an NT-proBNP > 900 pg/mL and evidence of AF at the time of the screening ECG and (ii) either (a) structural heart disease documented by report of left atrial enlargement or left ventricular hypertrophy, or (b) exhibiting symptom(s) of HF requiring treatment with diuretic(s) for at least 30 days prior to screening.

Group 3: Age \geq 55 years with 2 or more of the following:

- a. diabetes duration of \geq 10 years,
 - b. uncontrolled hypertension defined as SBP $>$ 140 mmHg despite 3 or more anti-hypertensive medications,
 - c. current smoking,
 - d. urine albumin:creatinine ratio (UACR) $>$ 30 mg/g,
 - e. eGFR of 45 to 60 mL/min/1.73 m², or
 - f. HDL $<$ 1 mmol/L (38 mg/dL)

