5.6 Concomitant Therapy

During the course of the study investigators will manage glucose, blood pressure and lipid levels according to local or regional standard of care guidance documents for the management of T2DM and cardiovascular risk factors/disease as issued by the relevant professional bodies (e.g. ADA, AHA, ESC, etc.). Subjects should be provided access to all additional therapies and interventions during the course of the study (including appropriate anti-platelet and anti-thrombotic therapies, PCI, etc.) if these are clinically indicated and approved by local competent authorities.

Subjects will be allowed to take medications or medicinal supplements prescribed to manage non-diabetic medical conditions during the study. Any concurrent medication or supplemental treatment of other, non-diabetes medical conditions should be continued at a stable dose and frequency for the entire study duration unless there is clinical reason to change the dose or frequency.

Blood pressure medications should not be altered during the screening period and the first 12 weeks of the main treatment period unless it is medically necessary to do so. If a change in treatment is required to appropriately manage hypertension or dyslipidemia during the run-in period, the subject may re-enter the screening after the clinical condition and treatment regimen have not changed for at least 4 weeks. If it is medically necessary to alter blood pressure medications during the first 12 weeks of the treatment period, new diuretic medications should not be initiated and the dose and frequency of existing diuretic medications should not be increased.

Subjects who do not meet protocol-specified glycemic targets at specified time points during the study will review diet and exercise counseling and/or receive rescue medication at the discretion of the investigator during the study. Anti-diabetic therapies prescribed to subjects for the purpose of treating hyperglycemia for more than 2 weeks will be considered rescue medications (see Prescribing Rescue Medication, above). Concomitant use of other SGLT2 inhibitors will not be permitted. A blood sample will be collected to measure the last HbA1c value prior to administration of any rescue medications. The rescue medications must be recorded as concomitant medications in the CRF.

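### SAP 6.2.8 has no exception for replacement, so a drug substitution is scored as relaxation, and SAP 6.2.7 then stops a later true intensification from being flagged

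*Combined protocol and SAP*

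**What the plan says.** SAP 6.2.8 gives two routes to relaxation. The first is "Stop or decrease dose of one or more oral hypoglycemic therapies occur during the double-blind treatment period". The second is a decrease of at least 5 units, worded as "unit total daily dose of insulin any time during the treatment period". There are two exclusions: "A decrease of hypoglycemic therapies after an intensification of hypoglycemic therapy use", and the end of a short course.

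SAP 6.2.7 lists five routes to intensification. They include a new oral agent added to prior medication, a new non-insulin injectable added to prior medication, "An insulin therapy is initiated in addition or in place of oral hypoglycemic therapy", and "An increase of ≥ 5 units total daily dose of insulin any time during the treatment period". Its first exclusion is "A replacement of a sulfonylurea or insulin with an injectable GLP-1 agonist". Its sixth says that an intensification following a relaxation is not counted.

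The two flags are used in:

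- the proportions with intensification and relaxation (SAP 8.2.2.4) and the times to first occurrence (8.2.2.6);
- the HbA1c and FPG over-time model (8.2.2.2), as a three-level covariate (no change, after relaxation, after intensification) with a treatment interaction;
- the tipping-point analysis, which sets HbA1c after intensification to missing, and the LOCF analysis, which overwrites it (8.1.2). Both are repeated for the insulin key secondary (8.2.1.4) and for the sulfonylurea subset (8.2.2.1).

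The primary analysis (8.1.1) keeps HbA1c values obtained after intensification.

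**The concern.** The stated objective is the proportion of subjects who require a relaxation of their regimen. A subject moved from one glucose-lowering drug to another has not shown that need. The first exclusion in 6.2.7 shows that the authors did not regard a switch to a GLP-1 agonist as stepping treatment up. Without a matching exclusion in 6.2.8, the same switch is recorded as stepping it down.

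The error also spreads. Once a switch is scored as relaxation, the sixth exclusion in 6.2.7 prevents any later step-up in that subject from being flagged. HbA1c values that the tipping-point and LOCF analyses are meant to remove then stay in, and in the over-time model they carry the wrong category.

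No later step in the current SAP would catch this. It contains no adjudication of these events, and its revision history records that the adjudication was taken out. The written rules are the classifier.

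**Working it through.** No figure in the plan bears on this point, so there is nothing to reproduce. The check applies the text of 6.2.7 and 6.2.8 to ordinary regimen changes, in date order and with both ordering exclusions.

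| Regimen change | Intensification (6.2.7) | Relaxation (6.2.8) |
|---|---|---|
| Sulfonylurea stopped, GLP-1 agonist started in its place | No (exclusion 1) | Yes (item 1) |
| Insulin (5 units or more) stopped, GLP-1 agonist started in its place | No (exclusion 1) | Yes (item 2) |
| Insulin started in place of an oral agent, same day | Yes (item 4) | Yes (item 1) |
| Oral agent stopped, insulin started next day | No (exclusion 6) | Yes (item 1) |
| Oral A stopped, oral B started next day | No (exclusion 6) | Yes (item 1) |
| Oral B started, oral A stopped next day | Yes (item 1) | No (exclusion 1) |
| Oral A stopped and oral B started, same day | Only if B is read as added | Yes (item 1) |
| Sulfonylurea to GLP-1 agonist, insulin started later | No (exclusion 6) | Yes (item 1) |
| Insulin 60 to 54 to 70 units/day | No (exclusion 6) | Yes (item 2) |
| Existing GLP-1 agonist: dose raised | No | No |
| Existing GLP-1 agonist: dose lowered or stopped | No | No |

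Four results follow.

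1. **Substitution.** The first two rows are relaxations only because 6.2.8 lacks the exclusion that 6.2.7 has.
2. **Order.** The same oral-for-oral switch is relaxation or intensification according to which date comes first. A one-day gap also decides whether insulin in place of an oral agent counts as intensification at all. For the same-day case both flags are met, and the three-level covariate in 8.2.2.2 has no rule for which level applies.
3. **Masking.** In the eighth row the later insulin start is never flagged. In the ninth, the dose ends 70 − 60 = 10 units above where it began, twice the 5-unit threshold, yet the subject is only relaxed. For the week-24 sensitivity analyses this matters only if both changes fall before week 24. The over-time model has no such limit.
4. **Gap.** Protocol inclusion criterion 5 allows GLP-1 agonists at entry. Item 3 of 6.2.7 covers only a new injectable, and 6.2.8 covers only oral agents and insulin.

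**Size.** The documents give no rate of switching, so any figure is an assumption. Suppose true relaxation is 8% on active and 4% on placebo: OR = (0.08/0.92)/(0.04/0.96) = 2.09. Adding falsely scored switches gives:

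- 3% active, 6% placebo: 11% v 10%, OR = (0.11/0.89)/(0.10/0.90) = 1.11;
- 3% in each arm: 11% v 7%, OR = (0.11/0.89)/(0.07/0.93) = 1.64;
- 6% active, 3% placebo: 14% v 7%, OR = (0.14/0.86)/(0.07/0.93) = 2.16.

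The result can move a long way or hardly at all, and in either direction, depending on rates that the plan does not state.

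**The case against.** The strongest reply is that little hangs on this. Both endpoints are exploratory with nominal p-values (8.2.2), the affected HbA1c analyses of the primary and insulin key secondary endpoints are sensitivity analyses, and the primary analysis retains the values in question. That stands and limits the weight of the point.

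A second reply is that the two ordering exclusions together stop changes on different dates from scoring as both. That is correct: double scoring is a same-day problem only. But the same exclusions make the result depend on date order and hide later intensifications.

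Third, an oral-for-oral swap may not be intensification, since item 1 speaks of adding a drug while item 4 speaks of adding or replacing. That is a fair reading of the same-day swap. It leaves the relaxation flag in place.

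A reader might also infer that the flat 5-unit insulin rule misclassifies changes that the protocol calls stable. Inclusion criterion 5 accepts less than 20% "variability in total daily insulin dose". Five units equals 20% only at 5/0.20 = 25 units/day; it is 5/60 = 8.3% at 60 units/day and 5/15 = 33% at 15. The documents do not support that inference. The 20% figure describes stability over the 3 months before entry. During treatment, protocol 5.2.5 counts any dose or frequency increase in a prior insulin regimen as rescue, so a 5-unit rise is not a misclassification by that definition. The SAP also neutralises as-needed insulin and short courses for acute illness, and doses come from a log of recorded changes, not from noisy repeated readings. What remains is that the passages disagree: 5.2.5 has no threshold, protocol 5.6 says that therapies "for the purpose of treating hyperglycemia for more than 2 weeks will be considered rescue medications", and the SAP uses 5 units without naming a reference dose.

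**Conclusion.** The point holds for substitutions, same-day and date-order effects, masked intensifications, and uncaptured changes to an existing GLP-1 agonist. These follow from the rules as written and need no assumption about the data.

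Their reach is the two regimen-change endpoints, the exploratory HbA1c and FPG over-time model, and the tipping-point and LOCF analyses, including those for the insulin key secondary. The relaxation rule itself removes no HbA1c data; it reaches the sensitivity analyses only through the sixth exclusion in 6.2.7. The primary analysis is untouched.

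It would be tempting to add that such switches are common, or that they cluster on placebo and so bias the relaxation comparison toward the null. The documents give no switch frequency, no split by arm and no distribution of insulin dose; they say only that about 50% of subjects are expected to be on insulin. Size and direction are therefore unknown. On insulin, the supportable finding is a set of unreconciled thresholds, not demonstrated misclassification.

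**What to change.** Before unblinding, amend the SAP as follows.

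- **6.2.8, replacement:** stopping or lowering an agent is not relaxation when another glucose-lowering agent is started or increased in its place.
- **6.2.7 and 6.2.8, same day:** a same-day change from an oral agent to insulin counts as intensification only.
- **6.2.7, exclusion 6:** limit it to a return to the baseline regimen, so that a step beyond baseline after a relaxation is flagged.
- **Non-insulin injectables:** add dose increases to 6.2.7, and dose decreases or stops to 6.2.8.
- **Insulin:** reconcile the 5-unit analysis threshold with protocol 5.2.5 and 5.6, state the reference dose from which a change is measured, and record any remaining difference in SAP section 12. No particular threshold is proposed here.

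The cost is SAP wording, reprogramming from the concomitant medication log, and somewhat fewer relaxation events, so slightly wider intervals for that endpoint. No new data are needed.
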